8.7 Premature termination of the study

Criteria for termination of the study prematurely: Since none or only minor side effects are expected, there is no specific criteria for premature termination of the study that can be stated beforehand. In the case of premature termination of the clinical trial, the investigator will inform

the reviewing accredited METC and the sponsor. Reasons for termination will be stated in writing.

All participants will be informed. Participants will receive usual care.

9. SAFETY REPORTING

9.1 Temporary halt for reasons of subject safety

In accordance to section 10, subsection 4, of the WMO, the sponsor will suspend the study if there is sufficient ground that continuation of the study will jeopardise subject health or safety. The sponsor will notify the accredited METC without undue delay of a temporary halt including the reason for such an action. The study will be suspended pending a further positive decision by the accredited METC. The investigator will take care that all subjects are kept informed.

9.2 AEs, SAEs and SUSARs

9.2.1 Adverse events (AEs)

Adverse events are defined as any undesirable experience occurring to a subject during the study, whether or not considered related to the investigational product. All adverse events reported spontaneously by the subject or observed by the investigator or his staff will be recorded.

9.2.2 Serious adverse events (SAEs)

A serious adverse event is any untoward medical occurrence or effect that at any dose:

- results in death;
 - is life threatening (at the time of the event);
 - requires hospitalisation or prolongation of existing inpatients' hospitalisation;
 - results in persistent or significant disability or incapacity;
 - is a congenital anomaly or birth defect;
 - Any other important medical event that may not result in death, be life threatening, or require hospitalization, may be considered a serious adverse experience when, based upon appropriate medical judgement, the event may jeopardize the subject or may require an intervention to prevent one of the outcomes listed above.
- An elective hospital admission will not be considered as a serious adverse event.

The investigator will report all SAEs to the sponsor without undue delay after obtaining knowledge of the events.

The sponsor will report the SAEs through the web portal *ToetsingOnline* to the accredited METC that approved the protocol, within 7 days of first knowledge for SAEs that result in death or are life threatening followed by a period of maximum of 8 days to complete the

initial preliminary report. All other SAEs will be reported within a period of maximum 15 days after the sponsor has first knowledge of the serious adverse events.

9.2.3 Suspected unexpected serious adverse reactions (SUSARs)

Adverse reactions are all untoward and unintended responses to an investigational product related to any dose administered.

Unexpected adverse reactions are SUSARs if the following three conditions are met:

1. the event must be serious (see chapter 9.2.2);
2. there must be a certain degree of probability that the event is a harmful and an undesirable reaction to the medicinal product under investigation, regardless of the administered dose;
3. the adverse reaction must be unexpected, that is to say, the nature and severity of the adverse reaction are not in agreement with the product information as recorded in:
 - Summary of Product Characteristics (SPC) for an authorised medicinal product;
 - Investigator's Brochure for an unauthorised medicinal product.

The sponsor will report expedited the following SUSARs through the web portal *ToetsingOnline* to the METC

- SUSARs that have arisen in the clinical trial that was assessed by the METC;
- SUSARs that have arisen in other clinical trials of the same sponsor and with the same medicinal product, and that could have consequences for the safety of the subjects involved in the clinical trial that was assessed by the METC.

The remaining SUSARs are recorded in an overview list (line-listing) that will be submitted once every half year to the METC. This line-listing provides an overview of all SUSARs from the study medicine, accompanied by a brief report highlighting the main points of concern.

The expedited reporting of SUSARs through the web portal Eudravigilance or ToetsingOnline is sufficient as notification to the competent authority.

The sponsor will report expedited all SUSARs to the competent authorities in other Member States, according to the requirements of the Member States.

The expedited reporting will occur not later than 15 days after the sponsor has first knowledge of the adverse reactions. For fatal or life threatening cases the term will be maximal 7 days for a preliminary report with another 8 days for completion of the report.

9.3 Annual safety report

In addition to the expedited reporting of SUSARs, the sponsor will submit, once a year throughout the clinical trial, a safety report to the accredited METC, competent authority, and competent authorities of the concerned Member States.

This safety report consists of:

- a list of all suspected (unexpected or expected) serious adverse reactions, along with an aggregated summary table of all reported serious adverse reactions, ordered by organ system, per study;
- a report concerning the safety of the subjects, consisting of a complete safety analysis and an evaluation of the balance between the efficacy and the harmfulness of the medicine under investigation.

9.4 Follow-up of adverse events

All AEs will be followed until they have abated, or until a stable situation has been reached.

Depending on the event, follow up may require additional tests or medical procedures as indicated, and/or referral to the general physician or a medical specialist.

SAEs need to be reported till end of study within the Netherlands, as defined in the protocol

9.5 Data Safety Monitoring Board (DSMB)

Not applicable.

10. STATISTICAL ANALYSIS

Primary and secondary study parameter(s)

Baseline characteristics will be described in detail per group in order to assess any imbalance. In case of missing data, we will use stochastic regression imputation to produce a synthetic part of the data to allow for an intention to treat analysis.

Per group, the post-treatment xerostomia score will be described as mean and standard deviation, or median and interquartile range in case of severe skewness. Additionally, we will compute a change-from-baseline score for both groups, which will be described in a similar matter. All secondary

outcome measures will be described in full using either mean and standard deviation or median and interquartile range for continuous measures, and count and proportion for categorical measures. For exploratory purposes, we will use the independent-samples t-test to test for differences in xerostomia complaint scores (NRS) between the two groups. However, as this is a pilot study, the emphasis will lie on clinical interpretation of the effect sizes of both groups separately. Preliminary analyses on secondary outcome measures will be performed using the independent samples t-test and Fisher's Exact test, depending on the measurement level of each variable.

Other study parameters

Not applicable.

Interim analysis

No interim analysis will be performed.

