3. STUDY DESIGN

DESIGN:

Open-label randomised controlled pilot study

PARTICIPANTS

The study will be performed at the outpatient clinic internal medicine/elderly care of the Maastricht University Medical Centre+.

INTERVENTION:

The intervention concerns the treatment of xerostomia in 2 treatment groups:

1. low dose pilocarpine = 3 x 2.0 mg = 3 x 2 drops of pilocarpine 20.0 mg/ml (2%) per day
2. high dose pilocarpine = 3 x 5.0 mg = 3 x 5 drops of pilocarpine 20.0 mg/ml (2%) per day

The study lasts 21 days of which the first 14 days with medication and the last 7 days without medication to measure a possible “switch-on” effect.

MEASUREMENTS

Xerostomia	Numeric Rating Scale (NRS) Geriatric Oral Health Assessment Index (GOHAI-NL)
Concurrent symptoms	Utrecht symptom Diary (USD)
Generic Health-Related Quality of Life (HRQoL)	EuroQoL 5D (EQ5D)
Global Perceived Effect (GPE)	GPE 7-point scale
Side effects	4-point Likert scale (flu-like symptoms, sweating, headache, urinary frequency, diarrhoea, nausea, vomiting, palpitations, dizziness, rhinitis, other)
Whole resting saliva	Total amount of unstimulated saliva measured in 5minutes

Patient characteristics that are collected at inclusion include gender, age, primary diagnosis, co-morbidity, medication and relevant history.

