8.3 Study procedures

The study will be performed at the outpatient clinic internal medicine/elderly care of the Maastricht University Medical Centre+. Potentially eligible patients will be identified on the outpatient clinic by answering the question if they have suffered from a dry mouth in the last three months. If the answer to this question is yes they will be invited to participate when meeting the inclusion criteria.

Each patient that participates in this study will receive a restaurant coupon and their travel expenses will be covered.

Randomisation will occur through a sealed envelope system. Once a patient has consented to the trial, a sealed opaque envelope is opened and the patient will receive the allocated treatment regime. This sealed opaque envelope will also contain a two digit number wherein the patient will be identified from this point forward in the database. The sealed opaque envelopes with all its content will be arranged by the researcher before start of the study.

Measures will be performed on day 0, 7, 14 and 21. Questionnaires on day 0, 7, 14 and 21, whole resting salivary flow on day 0 and 14, blood pressure will be measured on day 0 before and 1 hour after pilocarpine administration and on day 14.

	Day 0	Day 7	Day 14	Day 21
Hospital visit	X		X	
Patient characteristics	X			
Xerostomia NRS / GOHAI-NL	X	X	X	X
USD	X	X	X	X
EQ5D	X	X	X	X
GPE	X	X	X	X
Side effects	X	X	X	X
RR	X		X	
Whole resting saliva	X		X	

After inclusion the patient will visit the outpatient clinic twice on day 0 and day 14. On the first visit (day 0) after inclusion a questionnaire consisting of 45 questions, will be filled in, this will take 20 minutes. Also patient characteristics, including use of medication, will be accessed. Blood pressure and whole resting saliva will be measured. The blood pressure will be measured in sitting position using the Dinamap technology V100 care scape from general electric. The whole resting saliva will be measured by the doctor/research nurse. The patient will have to sit straight in a chair and will be asked to swallow the saliva that is currently in their mouth, in the next five minutes the patient will be asked to accumulate all the saliva that is spontaneously produced in their mouth. This whole resting saliva will be collected in a previously weighted cup and the result of each patient will be compared. The cups and the whole resting saliva will be measured with the SARTORIUS AC210p scale.

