8.4 Withdrawal of individual subjects

Subjects can leave the study at any time for any reason if they wish to do so without any consequences. The investigator can decide to withdraw a subject from the study for urgent medical reasons.

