8.4.1 Specific criteria for withdrawal

Unacceptable adverse effects.

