8.6 Follow-up of subjects withdrawn from treatment

Patients will receive usual care after withdrawal

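### Section 10 applies ordinary tests to data filled by stochastic regression imputation with no pooling, so imputed values count as observed patients and precision is overstated

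*Protocol*

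**What the plan says.** Section 10 handles missing data in one sentence: "we will use stochastic regression imputation to produce a synthetic part of the data to allow for an intention to treat analysis". It does not state the variables in the imputation model, the number of draws, or how the imputation enters the later analysis.

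For the dry-mouth score, "we will use the independent-samples t-test to test for differences in xerostomia complaint scores (NRS) between the two groups", labelled exploratory. Secondary outcomes get the same t-test or Fisher's exact test. The main reading is descriptive: "the emphasis will lie on clinical interpretation of the effect sizes of both groups separately". Section 4.4 justifies 12 patients per group by precision about the mean and variance, and intends the results as input to a later sample size calculation.

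On withdrawal, section 8.4 says "Subjects can leave the study at any time for any reason". Section 8.4.1 gives one specific criterion, "Unacceptable adverse effects". Section 8.6, headed as follow-up of subjects withdrawn from treatment, says "Patients will receive usual care after withdrawal" and nothing about measurements. Section 8.3 schedules "Questionnaires on day 0, 7, 14 and 21" without saying whether this depends on still taking the drops.

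**The concern.** A value drawn from a regression carries no information beyond the observed patients it was predicted from. If it enters a t-test as a 24th observation, the standard error is computed as though it did. The random residual keeps the spread of the data realistic, but it does not make the standard error account for the missing information. That requires several draws and a between-draw variance term.

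Two uses of the data are exposed: the between-dose test, and the precision attached to each arm's mean change. The second matters more here. The emphasis is on each group separately, and section 2 makes a clinically meaningful change the trigger for a placebo-controlled trial.

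There is also a side question. Section 10 says the imputation serves an intention-to-treat analysis. Whether it does depends on what is measured after a patient stops the drops, and section 8.6 leaves that open.

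**Working it through.** **Inputs from the protocol.** 12 per arm, 24 in total (sections 4.4 and 8.2); 2 × 12 = 24 reproduces the stated size, which is a rule of thumb and not a power calculation. The method and tests are those of section 10. No dropout figure is given for this trial. Section 1 cites 6% to 15% for systemic pilocarpine; on 24 patients that is 1.4 to 3.6. It is used only as an illustration, because section 8.7 expects no or only minor side effects.

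**Assumptions.** Two-sided 5% test, normal data, no true dose difference, missing at random, baseline–outcome correlation ρ = 0.5, 1 to 4 of 24 missing.

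**Why the standard error is too small.** Take m of n = 12 missing in each arm, with arm and baseline in the model. In outcome-SD units, and ignoring error in the slope, the variance of a completed arm mean is about

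ρ²/n + (1 − ρ²) × [1/(n − m) + m/n²].

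For m = 2: 0.25/12 + 0.75 × (1/10 + 2/144) = 0.0208 + 0.0854 = 0.1063. The SD of the difference is √(2 × 0.1063) = 0.461. Simulation gives 0.462 to 0.464. The t-test takes it to be √(2/12) = 0.408, too small by a factor of 0.461/0.408 = 1.13.

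**Size of the t-test** (simulation, nominal 5%; multiple imputation uses arm and baseline, 20 sets, Rubin's rules with small-sample degrees of freedom):

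| Missing of 24 | One imputation, arm in model | One imputation, arm omitted | Multiple imputation | Observed only |
|---|---|---|---|---|
| 1 | 5.8% | 5.1% | 4.8% | 5.0% |
| 2 | 6.7% | 5.0% | 4.7% | 5.1% |
| 3 | 7.5% | 5.0% | 4.4% | 4.9% |
| 4 | 8.5% | 5.0% | 4.3% | 5.0% |

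With 4 missing and arm in the model, the size is 9.2% at ρ = 0.3 and 7.5% at ρ = 0.7.

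**Why omitting arm is no remedy.** Imputed values in both arms then share one expected level. With 2 of 12 missing per arm, a true dose difference is multiplied by 10/12 = 0.83, a shrinkage of 17%. The test holds its size only because the imputation assumes no difference.

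**Per-arm precision.** A nominal 95% interval for an arm's mean change, using the completed SD and n = 12, covers 94.3%, 93.6%, 92.7% and 91.8% with 1, 2, 3 and 4 missing (arm in the model, averaged over the arms). With arm omitted and 4 missing it covers about 93.4%. Multiple imputation gives 95.7% to 96.6%.

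**The SD itself.** With arm in the model and data missing at random, the imputed SD of change is 0.998 to 1.002 times the true SD.

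**Intention to treat, conditional.** If a share f of an arm stops, is not measured afterwards, and loses a benefit of D points, imputing from patients still treated overstates that arm's mean change by f × D. With D = 2 assumed, this is 0.06 × 2 = 0.12 to 0.15 × 2 = 0.30 points. It is half that if half the benefit is lost, and zero if none is. For scale, the half-width of an arm's 95% interval at an assumed SD of 2 is 2.201 × 2/√12 = 1.27 points.

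**The case against.** The strongest reply is that section 10 fixes neither the imputation model nor the number of draws. Stochastic regression is also the step that multiple imputation repeats, so an analysis plan not seen here could supply the pooling. That stands as a condition: if it does, the point falls away. As written, however, the protocol names a method that ordinarily gives one data set and pairs it with ordinary tests, which is more than a missing detail.

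A reader might infer that the t-test is inflated whatever is done. The protocol does not support that: with arm omitted the size stays near 5%. Only the overstated per-arm precision holds under both models, and section 10 plans no confidence interval, so the coverage figures apply to an interval someone would have to compute.

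A reader might also infer that the variance passed to the later trial is wrong. With arm in the model and data missing at random, it is not.

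It is also fair to say that the test is exploratory, treatment lasts only 14 days, and four missing of 24 (17%) lies above even the borrowed dropout range. With one missing, the test runs at 5.8% against 5%. Analysing observed patients only holds the nominal level at least as well as multiple imputation, so the latter is not the only sound choice.

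**Conclusion.** The point holds as a modest flaw in the analysis: imputed values count as observed patients, and precision is overstated. With arm and baseline in the model, ρ = 0.5 and data missing at random, the nominal 5% test runs at about 6% to 8.5% for 1 to 4 of 24 missing. Coverage for an arm mean falls to about 92% with 4 missing, or about 93% with arm omitted. With complete data there is no effect.

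It is tempting to go further and say that the intention-to-treat claim is false because outcomes stop at withdrawal. The protocol does not say so. Section 8.6 is silent, and nothing in section 8.3 ends the questionnaires when the drops stop. A bias would need patients to stop, to go unmeasured, and to do worse than comparable completers. None of this is documented, and section 3 treats persistence off drug as an open question, with "the last 7 days without medication to measure a possible" an after-effect. Even then, the illustrative 0.12 to 0.30 points is small beside ±1.27. This part is a clarification worth making, not an error.

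**What to change.** In section 10, replace stochastic regression imputation with multiple imputation, with arm, baseline and the other time points in the model, pooled by Rubin's rules with small-sample degrees of freedom. Alternatively, analyse observed patients only. For outcomes tested with Fisher's exact test, to which Rubin's rules do not directly apply, report observed patients and the number missing.

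As a clarification, section 8.6 could state that patients who stop the drops but keep their consent still complete the scheduled questionnaires, by telephone if needed, and that these values enter the analysis. Without that, imputation from patients still on treatment matches intention to treat only if stoppers score like comparable completers.

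The cost is about two sentences in section 10, one in section 8.6 and a few questionnaires; calls on days 7 and 21 are already planned. With multiple imputation, per-arm intervals widen by about 6%, 9%, 13% and 18% with 1, 2, 3 and 4 missing, and the test becomes slightly conservative (4.3% to 4.8%). Patients who withdraw consent stay missing, so the change to section 8.6 does not help for them.

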2. OBJECTIVES

Objective

This study intends to deliver the “proof-of-concept” that locally administered pilocarpine drops in two doses are effective in a population of elderly (aged ≥ 70 years) with xerostomia at the expense of limited adverse events. To this end, the study aims to quantify the effect size of pilocarpine in two different dosages. In case we observe clinically meaningful changes in xerostomia through measured NRS, a sufficiently-powered RCT will be prepared to compare pilocarpine to placebo.

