4.2 Inclusion criteria

- ≥ 70 years of age
- Clinical diagnosis of chronic dry mouth defined as a Numeric Rating Scale (NRS) score ≥ 5 (scale 0 – 10, with 0 = no dry mouth and 10= worst possible dry mouth) on severity of xerostomia for more than 3 months.

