4.4 Sample size calculation

For this study we will take a pragmatic approach, as too little is known of the mean and variance of xerostomia complaints, quantified using the NRS, and the effect size of pilocarpine. This study will provide input for the sample size calculation for a future study. It would be feasible to include at least 24 patients in a period of 6 months, or 12 per group, as suggested as a rule of thumb for pilot studies to obtain sufficient precision about the mean and variance. [29]

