8. METHODS

8.1 Study parameters/endpoints

8.1.1 Main study parameter/endpoint

- change in xerostomia score (NRS)
- change in oral health-related quality of life (GOHAI-NL)

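### Minor: the exploratory NRS comparison between doses is an unadjusted t-test, although Day 0 NRS is collected and ANCOVA would be the safer choice

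*Protocol*

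**What the plan says.** Section 10 (Statistical analysis) describes the post-treatment NRS and the change from baseline for each group. For the comparison of the two doses it then says: "we will use the independent-samples t-test to test for differences in xerostomia complaint scores (NRS) between the two groups". It does not say which of the two scores is tested, names no day, and includes no covariate. Baseline imbalance is to be described, but no baseline-adjusted comparison appears anywhere in the protocol.

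The baseline value is planned for everyone. Section 8.3 sets "Questionnaires on day 0, 7, 14 and 21, whole resting salivary flow on day 0 and 14", and the NRS is one of those questionnaires. On timing, section 3 says: "The study lasts 21 days of which the first 14 days with medication and the last 7 days without medication".

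The same section 10 limits the weight of the test, since "the emphasis will lie on clinical interpretation of the effect sizes of both groups separately". Section 4.4 gives no SD or effect size, on the ground that "too little is known of the mean and variance of xerostomia complaints".

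**The concern.** A t-test on Day 14 NRS makes no use of the Day 0 score. A t-test on the change score uses it, but with a fixed weight of one, which costs precision when the Day 0/Day 14 correlation is well below the ratio of the two SDs. Which test is better depends on quantities that the protocol says are not known. ANCOVA estimates the weight from the data, and it gives the same dose effect whether the Day 14 score or the change is the outcome.

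With 12 patients per arm and no stratification mentioned, a chance difference in Day 0 NRS is a real possibility. At stake is the width of one exploratory interval. Validity is not in question, nor are the per-group effect sizes on which the pilot will be judged.

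**Working it through.** **The plan's own figure.** Section 4.4 gives 12 per group by a rule of thumb: 2 × 12 = 24. No alpha, power, SD or effect size is stated, so there is nothing further to reproduce.

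**Inputs from the protocol.** n = 12 per arm, N = 24 (sections 4.4 and 8.2), and NRS on Days 0 and 14 (section 8.3).

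**Assumptions (the protocol gives no values).** The within-group Day 14 SD is set to 1, and the slope is linear and common to both groups. The Day 0/Day 14 correlation r is 0.1, 0.3, 0.5 or 0.7. The SD ratio k = SD(Day 0)/SD(Day 14) is 1.0, 0.8 or 0.6. Values of k below 1 are included because entry requires "Clinical diagnosis of chronic dry mouth defined as a Numeric Rating Scale (NRS) score ≥ 5", which narrows the Day 0 range.

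**Per-patient variance**
- Post-score t-test: 1
- Change-score t-test: 1 + k² − 2rk = (1 − r²) + (k − r)²
- ANCOVA: (1 − r²) × (N − 3)/(N − 4) = (1 − r²) × 21/20 = 1.05(1 − r²)

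The second form of the change-score variance shows that it is never below 1 − r². ANCOVA's variance is therefore at most 1.05 times that of either t-test, for every r and k. Equality occurs at r = 0 against the post score and at r = k against the change score.

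**95% half-width** = t × √(variance × 2/12), with t(22) = 2.074 for the t-tests and t(21) = 2.080 for ANCOVA. For example, the post-score value is 2.074 × √(2/12) = 0.847. ANCOVA at r = 0.5 gives 2.080 × √(0.7875 × 2/12) = 0.753.

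| Half-width in Day 14 SD | r = 0.1 | r = 0.3 | r = 0.5 | r = 0.7 |
|---|---|---|---|---|
| Post-score t-test | 0.847 | 0.847 | 0.847 | 0.847 |
| Change-score t-test, k = 1.0 | 1.136 | 1.002 | 0.847 | 0.656 |
| Change-score t-test, k = 0.8 | 1.030 | 0.912 | 0.776 | 0.611 |
| Change-score t-test, k = 0.6 | 0.943 | 0.847 | 0.738 | 0.611 |
| ANCOVA | 0.866 | 0.830 | 0.753 | 0.621 |

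**What ANCOVA can gain**
- Against the post score: 0.847/0.621 = 1.36, so the post-score interval is up to 36% wider (r = 0.7).
- Against the change score at r = 0.1: 1.136/0.866 = 1.31 (k = 1.0), 1.030/0.866 = 1.19 (k = 0.8) and 0.943/0.866 = 1.09 (k = 0.6).

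**What ANCOVA can lose**
- Worst case: √1.05 × 2.080/2.074 ≈ 1.028, so an interval just under 3% wider than the better t-test's.
- Against the post score, its variance is higher when 1.05(1 − r²) > 1, that is, r < √(1 − 1/1.05) = 0.218.
- Against the change score, its variance is higher when (k − r)² < 0.05(1 − r²). That is r above 0.905 for k = 1.0, r from 0.626 to 0.898 for k = 0.8, and r from 0.395 to 0.748 for k = 0.6.

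**Simulation checks.** With 200,000 runs per cell at k = 0.6, the type I error of all three tests was 0.050 to 0.051. A second simulation used integer NRS scores with entry restricted to 5 or more, from an assumed unrestricted Day 0 mean of 6 and SD of 2. Assumed unrestricted correlations of 0.3, 0.5 and 0.7 fell to 0.22, 0.38 and 0.57. Standard errors in NRS points were then:

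| Unrestricted r | Post | Change | ANCOVA | Post/ANCOVA | Change/ANCOVA |
|---|---|---|---|---|---|
| 0.3 | 0.793 | 0.873 | 0.792 | 1.00 | 1.10 |
| 0.5 | 0.772 | 0.777 | 0.735 | 1.05 | 1.06 |
| 0.7 | 0.731 | 0.625 | 0.616 | 1.19 | 1.01 |

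In that simulation the two arms differed by 1 NRS point or more at Day 0 in about 10% of allocations.

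**The case against.** The strongest reply is that nothing here is an error. The t-test is valid, it is labelled exploratory, and section 2 ties the next step to something else: "In case we observe clinically meaningful changes in xerostomia through measured NRS, a sufficiently-powered RCT will be prepared". The contrast between doses is not part of that criterion. This stands, and it is why the point is minor.

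Second, covariates and test days are often left to an analysis plan, and none is at hand. That would answer the point if the protocol were silent, but section 10 names the test.

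Third, if the change score is what is tested, Day 0 is already used. This is correct as far as it goes. Section 10 leaves the choice open, so both readings were worked through, and each can lose precision.

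Fourth, the gain is assumed and may be small. The entry threshold lowers the correlation as well as the Day 0 SD, and under the restricted-entry simulation the gain over the better of the two t-tests was between nil and about 5%. This also stands. The figures of 36% and 31% are the upper ends of an assumed grid, not forecasts. The argument rests on the imbalance between a small capped loss and a possibly large gain, with no means of knowing in advance which t-test is the better one.

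Fifth, the 5% cap assumes 24 analysed patients, and section 8.5 does not replace withdrawals. With 18 analysed the factor is 15/14 = 1.07, so the cap becomes about 7%. The planned imputation of missing data is not reflected in these figures. Neither point reverses the comparison.

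**Conclusion.** The concern holds and is minor. Section 10 names a covariate-free t-test while the obvious covariate is already collected. ANCOVA costs at most about 5% in variance against the better t-test at N = 24. Over the assumed r and k, choosing the less suitable t-test costs up to about a third in interval width. The gain is likely to be nearer the low end if restricted entry brings the correlation down to about 0.2 to 0.4. All values of r, k and SD are assumptions, and the formulas need a linear common slope. The pilot's main conclusion is not affected.

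**What to change.** In section 10, replace the exploratory NRS t-test by ANCOVA of Day 14 NRS on dose group and Day 0 NRS, reported as an adjusted difference between doses with its 95% confidence interval. Name Day 14 (end of treatment) as the day tested. ANCOVA does not settle this by itself, and NRS is also measured on Day 21, after a week off drug. Do the same for GOHAI-NL, the other main endpoint in section 8.1.1. Keep the per-group descriptions as planned.

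The cost is one or two sentences, one degree of freedom and the small variance penalty shown above. No new data are needed.

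A clerical matter, independent of this point: section 10 marks its paragraph on other study parameters as not applicable, whereas section 8.1.3 lists salivary flow under that title. The two should be reconciled.
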